5.4 Pharmacokinetics

5.4.1 Collection of PK samples

Venous blood sampling for osimertinib PK: venous samples will be collected at selected time points to determine the PK of osimertinib and its metabolite, AZ5104 after single administration and at steady state.

Although every attempt should be made to collect all samples as per the CSP-defined time points, it is accepted that this will not always be possible and therefore it is essential that the actual time and date of collection of each blood sample (whether collected as per CSP or not) is recorded in the pCRF. See Section 5.8 for volume of samples to be collected.

Samples will be collected, labelled, stored, and shipped as detailed in the Laboratory Manual.

5.4.2 Determination of drug concentration

Samples for determination of the osimertinib and AZ5104 concentration in plasma and CSF will be analysed by Covance Laboratories on behalf of AstraZeneca, using appropriate bioanalytical methods. Full details of the analytical methods used will be described in a separate bioanalytical Report.

5.4.3 Storage and destruction of PK samples

Pharmacokinetic samples will be disposed of after the Bioanalytical Report finalisation or 6 months after issuance of the draft Bioanalytical Report (whichever is earlier), unless requested for future analyses.

Pharmacokinetic samples may be disposed of or destroyed and anonymised by pooling. Additional analyses may be conducted on the anonymised, pooled PK samples to further evaluate and validate the analytical method. Any results from such analyses may be reported separately from the Clinical Study Report (CSR).

[figure not shown]
Incurred sample reproducibility analysis, if any, will be performed alongside the bioanalysis of the test samples. The results from the evaluation will not be reported in the CSR but separately in a Bioanalytical Report.

Any residual back-up PK samples may be used for future **CCI** (in this case, residual back-up PK samples will be shipped to **PPD** (see details in the Laboratory Manual).

5.5 Pharmacodynamics (Not applicable)

5.6 Genetics (Not Applicable)

CCI

5.7.1 Collection of plasma and CSF samples

The following tissue/cytology samples will be taken:

- Formalin-fixed paraffin embedded tissue sample for biomarkers will be collected during screening (mandatory) and at progression (optional) for determination of the EGFRm status.

The following plasma samples will be taken:

- Venous blood sampling for biomarkers: blood samples will be collected at pre-administration of selected days from all patients for the determination of changes in ctDNA/exosomal DNA/RNA/protein at different days of treatment.
- Venous blood sampling for EGFR mutation detection in plasma: at baseline for confirmation for the presence of EGFRm status.

CSF sampling for ctDNA and exosomal DNA/RNA/protein:

- CSF samples (20 mL to be taken 2 to 3 times) will be collected at pre-administration prior to start of treatment and at the PET3 examination day for the analysis of ctDNA and exosomal DNA/RNA/protein. CSF samples may be collected during continued access treatment if disease progression in CNS.

5.7.2 Storage, re-use and destruction of biological samples

Samples will be stored for a maximum of 15 years from the date of the Last Patient's Last Visit, after which they will be destroyed. The results of this biomarker research will be reported either in the CSR itself or as an addendum, or separately in a scientific report or publication. The results of this biomarker research may be pooled with biomarker data from other studies with the IP to generate hypotheses to be tested in future research. Only the PI at the clinic has access to the code list kept locked under the current rules/regulations for each clinic. The samples are kept in an approved biobank at the study centre. CCI

The samples will be used only in the way that patients have approved for in their consents.

5.7.3 Labelling and shipment of biological samples

The PI ensures that samples are labelled and shipped in accordance with the Laboratory Manual and the Biological Substance, Category B Regulations (materials containing or suspected to contain infectious substances that do not meet Category A criteria), see Appendix 'IATA 6.2 Guidance Document'.

Any samples identified as Infectious Category A materials are not shipped and no further samples will be taken from the subject unless agreed with AstraZeneca and appropriate labelling, shipment and containment provisions are approved.

5.7.4 Chain of custody of biological samples

A full chain of custody is maintained for all samples throughout their lifecycle.

The Investigator keeps full traceability of collected biological samples from the patients while in storage at the centre until shipment or disposal (where appropriate) and keeps documentation of receipt of arrival.

The sample receiver keeps full traceability of the samples while in storage and during use until used or disposed of or until further shipment and keeps documentation of receipt of arrival.

AstraZeneca keeps oversight of the entire life cycle through internal procedures, monitoring of study centres and auditing of external laboratory providers.

Samples retained for further use are registered in the PPD [REDACTED] during the entire life cycle.

5.7.5 Withdrawal of Informed Consent for donated biological samples

If a patient withdraws consent to the use of donated biological samples, the samples will be disposed of/destroyed, and the action documented. If samples are already analysed, AstraZeneca is not obliged to destroy the results of this research.

As collection of the biological samples is an optional part of the study, then the patient may continue in the study.

The Investigator:

- Ensures patients' withdrawal of informed consent to the use of donated samples is notified immediately to AstraZeneca
- Ensures that biological samples from that patient, if stored at the study centre, are immediately identified, disposed of/destroyed and the action documented
- Ensures the organisation(s) holding the samples is/are informed about the withdrawn consent immediately and that samples are disposed of/destroyed, the action documented and the signed document returned to the study centre
- Ensures that the patient and AstraZeneca are informed about the sample disposal

AstraZeneca ensures the organisations holding the samples is/are informed about the withdrawn consent immediately and that samples are disposed of/destroyed and the action documented and returned to the study centre.

5.8 Volume of blood

The number of blood samples that will be drawn from each patient is shown in Table 3. Additional details will be described in a separate Laboratory Manual.

Table 3 Volume of blood to be drawn from each patient

Assessment	Sample volume (mL)	No of samples	Total volume (mL)
Blood chemistry	2.7	5	13.5
Coagulation	1.8	3	5.2
Haematology	2.7	5	13.5
Serology	1.8	1	1.8
Osimertinib PK	2	10 (5×2)	20
Biomarkers	20	5	100
EGFR mutation	20	2	40
Arterial blood radioactivity measurements	25	2 (or 3)	75 (or 100)
Arterial blood radioactivity and metabolite measurements (manual blood samples)	2	20 (or 30)	40 (or 60)
Arterial blood radioactivity and metabolite measurements (manual blood samples)	4	8 (or 12)	32 (or 48)
Venous blood radioactivity and metabolite measurements	4	18 (or 24)	72 (or 108)
Total	86	79 (100)	413 (or 510)

ABSS: Automatic blood sampling system; PET: Positron emission tomography; PK: Pharmacokinetics.

Note: arterial blood sampling includes ABSS used for the first 5 minutes, 5 mL/min. Manual blood samples will be in the range of 2 to 4 mL, not exceeding 40 mL. The study will include 2 PET examinations with arterial blood sampling and the third PET examination may omit arterial blood sampling.

Additional 50 mL blood may be drawn if repeated laboratory tests are needed or if PET examination protocol needs adjustment. The maximum volume to be drawn from each patient will not exceed 550 mL.

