s Arterial blood sampling for [¹¹C]osimertinib will occur at approximately 2, 4, 6, 8, 10, 15, 20, 30, 40, 50, 60, 75, and 90 minutes post-[¹¹C]osimertinib injection. Venous blood samples will be collected at 30, 60 and 90 minutes. In case of failure to sample arterial blood (eg, spasm, occlusion) the arterial blood sampling may be substituted by venous blood samples throughout the PET examination. The blood sampling schedule may be adjusted at the Investigator's discretion, but will not exceed 120 mL per patient per measurement (see point i, in case of failure of arterial sampling).

t If a patient cannot undergo the PET examination at the scheduled time or if technical failure occurs, eg, camera breakdown or radioligand synthesis failure, the patient will be discharged and the visit rescheduled to a later time point. PET examinations will continue over 90 minutes (minimum 60 minutes). If examination duration becomes shorter due to the technical or patient-related reasons, the data will be inspected and if quantitative analysis will not be possible, the measurement maybe rescheduled. In case of radiosynthesis failure and if radioactivity available for injection will be below 200 MBq (per 70 kg body weight), the PET examination will be rescheduled and the patient will be invited to participate on an additional visit. In case of technical failure on examination days, please contact AstraZeneca for alternate examination days.

u Osimertinib 80 mg once a day will be taken by the patient from the day of the second PET examination for at least 21 days before the PET3 examination will be scheduled. On Day 14 (± 2 days), a clinical visit to evaluate the safety of the patient will be performed.

v AEs will be assessed. SAEs will be collected from the time of signature of informed consent throughout the treatment period and including the follow up period. AEs will be collected throughout the study, from informed consent until the end of the follow up period. The follow-up period is defined as 30 working days after the IP is discontinued.

w A post study assessment will be performed within 30 working days after the IP has been infused and last PET examination completed. In the event of a holiday or weather delay, the follow-up visit may be postponed 1 to 2 working days (see Section 4.4).

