5.3.2.2 PET examination procedures

The PET examinations will be performed at the PET centre, Karolinska Institutet, Department of Clinical Neuroscience, PPD ██████████, Solna, Sweden.

PET examinations will include radioactivity measurements in blood and in the brain. Prior to brain PET examinations, a plastic helmet will be made for each patient individually for use during the PET examinations in order to minimize head movement. Brain PET examinations will be performed using a HRRT PET system (Siemens Molecular Imaging, Knoxville, TN, US). The patient will be placed recumbent with his/her head in the PET system. After the IV injection of [¹¹C]osimertinib emission data will be acquired in list mode over 90 minutes.

During the PET examination time, a series of arterial blood samplings will be taken to measure radioactivity and radiometabolites of [¹¹C]osimertinib. The purpose of blood measurements is to obtain a metabolite-corrected arterial input function which is used for the kinetic compartment analysis of [¹¹C]osimertinib brain exposure. The anaesthesiologist will perform the Allen's test to make sure there is normal flow in the wrist between radial and ulnar arteries. An arterial cannula will be inserted in the radial or brachial artery of 1 of the arms (the non-dominant arm if possible) under local anaesthesia. A venous cannula will be inserted in another arm for the administration of [¹¹C]osimertinib .

An arterial cannula will be used for arterial blood sampling during the PET examination time (first 10 minutes automatic blood sampling system [ABSS], followed by manual blood samples according to predefined KI PET centre protocol; at approximately 2, 4, 6, 8, 10, 15, 20, 25, 30, 40, 50, 60, 75 and 90 minutes post-[¹¹C]osimertinib injection). A venous cannula will be used for the bolus injection of [¹¹C]osimertinib, after it is dissolved in a sterile physiological phosphate buffer (pH 7.4). The mass of the tracer injected per single measurement will be less than 10 µg, the radioactivity per single injection will not exceed 330 MBq/70 kg of body weight. The cannula will be immediately flushed with 10 mL saline.

The collection of arterial and venous samples is required at PET1 and PET2 examinations for analysis. However, based on the preliminary data analysis in the first microdosing study in healthy patients, arterial assessments may be removed for PET3 examination.

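### Three rows of the Table 3 blood volumes do not multiply out and the sampler duration conflicts (5 versus 10 minutes); separately, the 7 mSv itemisation uses a flat 300 MBq and thorax-only CT

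*Protocol*

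**What the plan says.** **Blood.** Protocol Section 5.8, Table 3, lists sample volume, number of samples and total volume by assessment. The figures in brackets apply if the third PET also has arterial sampling. The printed totals are 79 (100) samples and 413 (or 510) mL. The note under the table states:

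- "arterial blood sampling includes ABSS used for the first 5 minutes, 5 mL/min"
- "the third PET examination may omit arterial blood sampling"
- "Additional 50 mL blood may be drawn if repeated laboratory tests are needed"
- "The maximum volume to be drawn from each patient will not exceed 550 mL"

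Section 5.3.2.2 describes the same arterial sampling as "first 10 minutes automatic blood sampling system [ABSS", followed by manual samples "at approximately 2, 4, 6, 8, 10, 15, 20, 25, 30, 40, 50, 60, 75 and 90 minutes". Table 1, footnote s, states "Venous blood samples will be collected at 30, 60 and 90 minutes". It lets the schedule be adjusted, "but will not exceed 120 mL per patient per measurement".

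**Radiation.** Section 1.3.1 adds three PETs at 300 MBq each (3.465 mSv) and two CTs at a thorax dose of 0.8 mSv each (1.6 mSv), and states a ceiling of 7 mSv. The same section calls the CTs thorax/abdomen examinations, and Section 5.1 adds the pelvis where there is disease. Sections 1.4 and 7.2 scale the activity to body weight: 300 MBq per 70 kg as target and 330 MBq per 70 kg as maximum. Section 3.1, criterion 10, admits patients up to 100 kg with a BMI up to 30.

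**The concern.** Table 3 is the only place where the protocol adds up the blood taken from a patient, and it sits beside a hard cap. If its rows do not multiply out, staff and the ethics committee cannot tell what volume is planned or whether the contingency fits under the cap. The sampler conflict matters more in practice than the slips in the table, because it changes how much blood is drawn at each arterial PET. The radiation ceiling raises a similar question: the listed items are not the activity and CT field that the protocol allows. These are limits on patient burden; no estimate, summary or analysis set depends on them.

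**Working it through.** **1. Reproduce the printed totals (Table 3).** The seven non-PET rows as printed: 13.5 + 5.2 + 13.5 + 1.8 + 20 + 100 + 40 = 194.0 mL.

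- Two arterial PETs: 194.0 + 75 + 40 + 32 + 72 = 413.0 mL.
- Three arterial PETs: 194.0 + 100 + 60 + 48 + 108 = 510.0 mL.
- Sample counts: 31 + 2 + 20 + 8 + 18 = 79, and 31 + 3 + 30 + 12 + 24 = 100.

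The printed totals are exact sums of the printed rows, so the digits were read correctly and the errors lie in the rows.

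**2. Volume × number, row by row.**

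| Row | Product (mL) | Printed (mL) |
|---|---|---|
| Coagulation | 1.8 × 3 = 5.4 | 5.2 |
| Automatic arterial sampler | 25 × 2 (or 3) = 50 (or 75) | 75 (or 100) |
| Venous, three PETs | 4 × 24 = 96 | 108 (= 4 × 27) |

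All other entries multiply correctly, including the two-PET venous figure (4 × 18 = 72).

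**3. Corrected totals on Table 3's own counts.** The non-PET rows become 194.2 mL.

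- Two arterial PETs: 194.2 + 50 + 40 + 32 + 72 = 388.2 mL (printed figure 24.8 too high).
- Three, 24 venous samples: 194.2 + 75 + 60 + 48 + 96 = 473.2 mL (36.8 too high).
- Three, 27 venous samples: 194.2 + 75 + 60 + 48 + 108 = 485.2 mL (24.8 too high).

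**4. Against the 550 mL cap.** Printed: 510 + 50 = 560 mL, above the cap. Corrected, plus 50: 438.2, 523.2 and 535.2 mL, all below it.

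**5. Which counts are right?** The printed count of 100 supports 24 venous samples (27 would give 103). The printed 108 mL supports 27, as does 18/2 = 9 per PET if the 18 belong to two PETs. Footnote s plans 3 per PET. Manual arterial samples are (20 + 8)/2 = (30 + 12)/3 = 14 per PET, matching the 14 times in 5.3.2.2, but footnote s lists 13. Table 1 also differs from Table 3 elsewhere:

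- Safety laboratory tests are marked at six visits: chemistry 6 × 2.7 = 16.2, haematology 16.2, coagulation 6 × 1.8 = 10.8 mL.
- PK has four times at two visits (footnote o): 8 × 2 = 16 mL.
- EGFR blood is 2 × 10 = 20 mL, at screening only (footnote q).

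The Table 1 base is 16.2 + 16.2 + 10.8 + 1.8 + 16 + 100 + 20 = 181.0 mL.

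**6. Sampler duration.** 5 min × 5 mL/min = 25 mL per PET. Section 5.3.2.2 gives no rate; assuming 5 mL/min for 10 minutes, it is 50 mL. Manual arterial samples add 10 × 2 + 4 × 4 = 36 mL per PET. Three arterial PETs with the 10-minute sampler, in mL:

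| Venous per PET | Per PET | Total, base 194.2 | Plus 50 | Total, base 181.0 | Plus 50 |
|---|---|---|---|---|---|
| 3 | 98 | 488.2 | 538.2 | 475.0 | 525.0 |
| 8 | 118 | 548.2 | 598.2 | 535.0 | 585.0 |
| 9 | 122 | 560.2 | 610.2 | 547.0 | 597.0 |

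With two arterial PETs and the 10-minute sampler: 388.2 + 50 = 438.2 mL; plus the contingency, 488.2; plus nine venous samples at PET3 (36 mL), 524.2. The cap holds throughout.

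**7. Radiation.** Printed items: 3 × 300 × 3.85 µSv = 3.465 mSv, plus 1.6, gives 5.065 mSv, leaving 1.935 mSv below the ceiling. With the coefficient fixed at 3.85 µSv/MBq and thorax-only CT:

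- Target activity at 100 kg: 3 × (300 × 100/70) × 3.85 µSv = 4.95; plus 1.6 = 6.55 mSv.
- Maximum activity at 100 kg: 3 × (330 × 100/70) × 3.85 µSv = 5.445; plus 1.6 = 7.045 mSv.
- Weight at which maximum activity reaches 7 mSv: (7 − 1.6)/(3 × 0.00385) × 70/330 = 99.2 kg.

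Room left per CT for an abdominal field at target activity: (7 − 5.065)/2 = 0.97 mSv at 70 kg and (7 − 6.55)/2 = 0.225 mSv at 100 kg. The documents give no abdominal CT dose.

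**The case against.** The best reply is that these are proofreading slips that overstate the volume on balance, and that the cap is mandatory while the extra 50 mL is optional. That stands. A reader might infer from 560 mL that patients would be over-drawn; the documents do not support this, because the cap controls and the corrected totals plus 50 mL fit under it.

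A reader might also infer that the two blood limits are incompatible, since three PETs at the full 120 mL give 194.2 + 360 = 554.2 mL. That rests on Table 3's non-PET counts. On the Table 1 base the sum is 181.0 + 360 = 541.0 mL, which fits. Likewise, the 1.8 mL left under the cap at 548.2 mL becomes 15 mL on the Table 1 base. The 122 mL that passes the per-PET limit needs both the assumed rate and nine venous samples; with the three samples in the footnote that sets the limit, it is 98 mL. Neither a conflict between the limits nor a replacement for 120 mL can be derived yet.

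On radiation, a reader might infer that the 7 mSv ceiling is broken. The gap above 5.065 mSv covers maximum activity up to about 99 kg. The only excess that can be computed is 0.045 mSv, at 100 kg with three upper-limit injections and a coefficient that does not vary with weight. If dose per MBq fell in proportion to weight, the total would be 5.445 × 0.7 + 1.6 = 5.41 mSv. No excess from the abdominal field can be stated.

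**Conclusion.** Minor, and certain as to the arithmetic. Three rows of Table 3 are internally wrong, the printed totals carry those errors, and the larger total with its contingency contradicts the cap in the same note by 10 mL. The 5-versus-10-minute conflict is a real ambiguity in procedure. If 5 mL/min applies for the full 10 minutes, the 50 mL contingency does not fit at three arterial PETs with 8 or 9 venous samples each, on either base; with 3 venous samples, or with only two arterial PETs, it does. The true venous count is undetermined. The radiation point is smaller and separate: the items listed are not the maximum weight-scaled activity or the full CT field, but no breach of the ceiling is established.

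**What to change.** In the next protocol amendment:

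1. Correct the coagulation and sampler rows, make the three-PET venous count and volume agree, and restate the totals.
2. Reconcile Table 3 with Table 1: venous samples per PET (3 versus 8 or 9), manual arterial times (14 versus 13), and the PK, EGFR and safety laboratory counts.
3. Give one sampler duration and rate in Sections 5.8 and 5.3.2.2.
4. Then check the 120 mL per-PET and 550 mL per-patient limits against the reconciled total, with the 50 mL contingency and with arterial sampling at PET3.
5. Restate the Section 1.3.1 itemisation at the maximum weight-scaled activity and for the full thorax/abdomen field, and give that figure to the radiation committee.

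The cost is protocol wording; the restated radiation figure may look less favourable. The SAP needs no change.

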6. SAFETY REPORTING AND MEDICAL MANAGEMENT

The Investigator is responsible for ensuring that all staff involved in the study are familiar with the content of this section.

6.1 Definition of adverse events

An AE is the development of any untoward medical occurrence in a patient or clinical study patient administered a medicinal product and which does not necessarily have a causal relationship with this treatment. An AE can therefore be any unfavourable and unintended sign (eg, an abnormal laboratory finding), symptom (for example nausea, chest pain), or disease temporally associated with the use of a medicinal product, whether or not considered related to the medicinal product.

The term AE is used to include both serious and non-serious AEs and can include a deterioration of a pre-existing medical occurrence. An AE may occur at any time, including run-in or washout periods, even if no IP has been administered.

6.2 Definitions of serious adverse event

A SAE is an AE occurring during any study phase (ie, run-in, treatment, washout, follow-up), that fulfils 1 or more of the following criteria:

- Results in death.
- Is immediately life-threatening.
- Requires in-patient hospitalisation or prolongation of existing hospitalisation.
- Results in persistent or significant disability or incapacity.
- Is a congenital abnormality or birth defect.
- Is an important medical event that may jeopardise the patient or may require medical intervention to prevent 1 of the outcomes listed above.

For further guidance on the definition of a SAE, see **Error! Reference source not found.** to the CSP.

6.3 Recording of adverse events

6.3.1 Time period for collection of adverse events

Adverse Events will be collected throughout the study, from informed consent until the end of the follow up period. Serious AEs will be collected from the time of signature of informed consent throughout the treatment period and including the follow up period. The follow-up period is defined as 30 working days after the IP is discontinued. SAEs occurring in the follow-up period should be reported to AstraZeneca in the usual manner (see Section 6.4).

6.3.2 Follow-up of unresolved adverse events

Any AEs that are unresolved at the patient's last visit in the study are followed up by the Investigator for as long as medically indicated, but without further recording in the pCRF. AstraZeneca retains the right to request additional information for any patient with ongoing AE(s) at the end of the study, if judged necessary.

If an Investigator learns of any SAEs, including death, at any time after a patient has completed the study and he/she considers there is a reasonable possibility that the event is related to osimertinib, the Investigator should notify AstraZeneca.

If patients who are gaining clinical benefit are allowed to continue the IP following data cut-off and/or post study completion then, as a minimum, all SAEs must continue to be collected and reported to AstraZeneca Patient Safety or its representative within the usual timeframe.

